Research Design/Plan: We propose a randomized, double-blind, trial of TMS to the left dorsolateral prefrontal cortex (DLPFC) for patients with MDD all of whom at the patient's treatment clinic are concurrently receiving pharmaceutical and psychotherapeutic interventions. Subjects will undergo TMS treatments for at least 4 weeks, but the duration of their TMS treatments may be extended (e.g. up to 8 weeks of treatment) if approved by the subject's third-party insurance plan. Arm 1 delivers active rTMS to the left DLPFC using the standard aiming strategy. Arm 2 delivers active rTMS to the left anterior DLPFC using connectivity-based, image-guided aiming. Arm 3 delivers active rTMS to the left posterior DLPFC using connectivity-based, image-guided aiming. In all three arms, rTMS is administered in an image-guided, robotically-positioned TMS (iTMS) manner to ensure therapist blinding and equivalent subject experiences across arms. In all three arms, the following stimulation protocol will be used: 10 Hz iTMS delivered in 4 sec trains with 26 sec inter-train intervals, 37.5 minutes/session (i.e. 3,000 pulses/session), 5 sessions/week, for at least 4 weeks. Neuroimaging will be used both for treatment planning and to characterize any TMS-induced network plasticity using resting-state functional magnetic resonance imaging (rs-fMRI) at week 4 of each treatment arm. Clinical assessments will be administered weekly throughout treatment at the subject's treatment clinic. Additional psychological tests will be performed at UT Health—San Antonio's Research Imaging Institute (RII) at the baseline and post-treatment visits in order to track subject progress.

Clinical Relevance: This will be the first study to determine the clinical effects of connectivity-guided iTMS in the treatment of MDD, to provide clues about the ideal neural networks (anterior DLPFC vs. posterior DLPFC) to target for more robust clinical outcomes, and to identify potential biomarkers of treatment response including changes in brain networks connectivity.

Item 3 Background	

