
Item 4 Purpose and rationale Insert purpose, objectives and research questions/hypotheses here. If you cut and paste from another document, make sure the excerpted material answers the question
	
We propose a randomized, double-blind, trial of iTMS to the left DLPFC for patients with MDD receiving treatment at the treatment clinic. In addition to treatment as usual, subjects will be randomized to receive iTMS in one of three treatment arms: Arm 1 delivers active iTMS to the left DLPFC using the SOC aiming strategy. Arm 2 delivers active iTMS to the left anterior DLPFC using connectivity-based, image-guided aiming. Arm 3 delivers active iTMS to the left posterior DLPFC using connectivity-based, image-guided aiming. In all three arms, repetitive TMS (rTMS) is administered in an image-guided, robotic manner to ensure therapist blinding and equivalent subject experiences across arms. In all three arms, the following stimulation protocol will be used: 10 Hz iTMS delivered in 4 sec trains with 26 sec inter-train intervals, 37.5 minutes/session (i.e. 3,000 pulses/session), 5 sessions/week, for at least 4 weeks. Neuroimaging will be used both for treatment planning and to characterize any TMS-induced network plasticity using resting-state fMRIs (rs-fMRIs) at week 4 of each treatment arm. Clinical assessments will be administered weekly throughout the TMS Treatment Phase. rs-fMRIs will be used both for treatment planning (baseline imaging), which guides the individualized positioning of the TMS coil, and to characterize iTMS-induced network connectivity (week 4). Clinical assessments using relevant clinician rated and self-report scales will be done weekly at the subject's treatment clinic. Other psychological tests will be performed at baseline, and week 4 when participants go to the RII for neuroimaging. Also, 1 and 3-month post-treatment clinical follow-ups will be conducted either in-person or over the phone to evaluate maintenance of clinical outcomes. If a subject's third-party insurance provider approves TMS treatment for more than 4 weeks, clinical assessments should continue on a weekly schedule and the 1 and 3-month post-treatment clinical follow-ups will be conducted (at their respective intervals) following that subject's last TMS treatment session.
 
Aim 1. In persons with drug-resistant MDD compare the treatment efficacy of connectivity-image-guided rTMS targeting anterior DLPFC (Arm 1), posterior (Arm 2) DLPFC and the FDA-approved SOC rTMS targeting protocol (Arm 3). In all 3 arms, at least 4 weeks (5 days/week) of the FDA-approved SOC stimulation protocol (10 Hz x 37.5 minutes) will be used.
 
 • Hypothesis 1a. Connectivity-based iTMS to the anterior left DLPFC will be superior to connectivity-based rTMS to the posterior left DLPFC and standard of care iTMS to the left DLPFC in relieving MDD symptoms. • Hypothesis 1b. Connectivity-based rTMS to the posterior left DLPFC will be superior to the standard of care iTMS to the left DLPFC in relieving MDD symptoms. 
Aim 2. Test for rTMS-induced changes in network functionality (plasticity) using rs-fMRI.
 
 • Hypothesis 2a. Intrinsic connectivity will be attenuated by active iTMS in networks connected to the respective treatment sites, as tested by correlation with the number of sessions received at the time of scanning and by pre-treatment-to-post-treatment contrast. • Hypothesis 2b. Treatment-induced decreases in connectivity will correlate with symptom improvement within and across treatment arms.

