irTMS Treatment Sessions. All participants will continue with their TAU at the subject's treatment clinic including regular medication management, encounters with their attending psychiatrist, and therapy sessions. An effort will be made to limit the disruptions in subjects' TAU by working research assessments and irTMS treatment sessions around their expected TAU programming. irTMS treatment visits will take place at their treatment clinic starting as soon as possible after the treatment plan is completed, expected to be 1-10 working days following baseline scanning. At the respective TMS treatment target site, the treatment clinician's team will deliver rTMS using the FDA-approved rTMS treatment protocol for MDD. This TMS protocol consists of 4 seconds of 10 Hz rTMS followed by a 26 second rest period; the treatment lasts for a total of 37.5 minutes (e.g. 3,000 rTMS pulses/session). Treatment is 5 days per week for at least 4 weeks in all arms. All treatments will delivered using a liquid cooled figure-8 MagPro coil (MagVenture, Denmark). If study participants decide that they cannot tolerate the prescribed dose of irTMS (e.g. 120% of resting motor threshold), they will be withdrawn from the study (see Discontinuation and Withdrawal of Patients Section below).

Phase II: Post-Treatment Follow-Up

Post-treatment MRI. Immediately following the last irTMS treatment at the end of the 4th week, a second functional MRI scan will be conducted to assess treatment effects. The post-MRI will occur any time after last treatment with up to a 3-day window for completion. After the post-treatment MRI session, each subject will also undergo another brief motor threshold assessment in order to document any changes—which may be used to report on the safety of this TMS treatment protocol. This second scanning visit should take approximately 1 hour.

Participant Blind Form. The Participant Blind Form measures the participant's best guess about the study treatment that they received, level of confidence in this guess, and how unblinding could potentially have occurred. This form will be used at treatment completion and follow-up for all of the RII's double-blind irTMS studies.

Independent Evaluator Blind Form. The Independent Evaluator Blind Form measures the independent evaluator's best guess about the study treatment that the subject received, level of confidence in this guess, and how unblinding could potentially have occurred.

Phase III: 1 Month/3 Month Follow-Up

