One month and three months after the final irTMS treatment session, participants will be interviewed (either in-person or over the telephone) by a member of the research team. Results from these assessments will be stored on the RII's secure XNAT server..

Table of Study Procedures:

Phase	Pre-Study			TMS Treatment Phase (at the clinic & the RII)				Post-Treatment (at the RII)	1 Month/ 3 Month Follow-Up (in-person or via telephone)
	Clinic Intake	Baseline	MRI Appt	Wk 1	Wk 2	Wk 3	Wk 4	Wk 5	Wk 8/Wk16
Review Medical History	X								
Informed Consent		X							
Metal Screening		X							
Patient Health Questionnaire-9 (PHQ-9)		X		X	X	X	X	X	X
Montgomery-Ashberg Depression Rating Scale (MADRS)			X					X	X
Adverse Events Monitoring			X	X-X	X-X	X-X	X-X	X	X
Concomitant Medications/Treatment		X		X-X	X-X	X-X	X-X	X	X
Structural MRI			X						
Intrinsic Connectivity by Blood- Oxygen-Level-Dependent Functional MRI			X					X	
Motor threshold assessment			X					X	
irTMS Treatment (at least 20 weekdays)				X-X	X-X	X-X	X-X		
Participant Blind Form							X		
Independent Evaluator Blind Form							X		

Data Protection. Data will be coded using an assigned number. Data collected during treatment will be placed into locked cabinets at the subject's treatment clinic's offices. Every member of the research team will be trained and monitored about how to handle and protect both medical and research records. Furthermore, the research team strictly controls access to study data. No identified data (either copies or originals) will be maintained at the study site. The study site will maintain a list of assignment numbers for the purpose of linking subsequent research materials.

Risk/Benefit Assessment.

Risks and Side Effects related to the irTMS applied to Dorsolateral Prefrontal Cortex Brain Region:

- Likely, some may be serious. In 100 people, approximately 20-30 may have:
 - Mild headache
 - Scalp and/or Facial pain/discomfort
 - Scalp and/or Facial Muscle Twitching
 - Neck pain
- Less Likely, some may be serious. In 100 people, approximately 5-10 may have:
 - Dizziness
 - Sleepiness
- Rare and Serious. In 100 people, approximately 1-2 may have:
 - Seizures

Risks and Side Effects related to the Robot placement of the irTMS include those which are:

- Rare and Serious. In 100 people, approximately 0-1 may have:

- Physical injury from the robotic device.

Risks and Side Effects related to the MRI include those which are:

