- To emotional distress during psychological assessments. All clinical staff associated with assessment have experience in psychiatric evaluation and will implement protocol procedures in a sensitive and supportive manner. Interviews will be stopped if subjects become distressed or object to answering questions. Measures implemented to minimize risks are: 1) Before participating, subjects undergo careful psychiatric and medical evaluation. 2) An experienced study clinicians are available at all times during the sessions to provide medical a psychiatric monitoring for subjects experiencing any difficulties during treatment. 3) All subjects will be seen weekly for ongoing assessment of behavioral symptoms. 4) If a subject’s clinical condition significantly worsens, he or she will be withdrawn from the research protocol to continue TAU at their treatment clinic. Any indication that a participant’s suicidality has worsened from baseline will be handled using processes at their treatment clinic.
- To breach of confidentiality. Study participants will be treated in individual offices located at their treatment clinic. Data a will be stored by an assigned participant code number so that data records and specimens can be viewed by password-authenticated, authorized investigators and Consortium personnel. Digital audio recordings of assessments will be labeled with the participant’s study id number and saved on a secure password protected server. Those recordings to be reviewed for fidelity to ensure that the assessment is being delivered in accordance with Consortium standardized procedures. There is no option for the reviewers to download or otherwise save the recordings to their computers. Every member of the Research Team will be trained and monitored about how to handle and protect both medical and research records. Only authorized study staff, and members of the Data Management and Biostatistics Core will have access to either the raw data or electronic study data.

Potential Benefits.

- The potential benefit to participants is the potential for MDD symptom relief.

Adverse Events, Unanticipated Problems, and Deviations.

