Clinical Outcomes Data Analysis plan. All pre-treatment and post-treatment MRIs will be acquired and analyzed at the RII, however, all of the statistical analysis of the symptom scores for this project will be done upon completion of recruitment and termination group blinding. The primary efficacy outcome measure will be the PHQ-9 for MDD symptoms assessed pre-treatment, weekly during treatment, post-treatment, and 1/3-months following the completion of treatment and the MADRS for the diagnosis of MDD assessed pre-treatment, post-treatment, and 1/3-months following the completion of treatment. The primary analysis will use

mixed effects regression models. Secondary analysis will focus on changes in MDD symptoms clusters, effects of the intervention in mood symptoms, functioning and cognitive outcomes. Types and rates of adverse events will be summarized and compared across the study groups. The durability of benefit and the clinical significance of PHQ-9 changes will be explored. Non-compliance to protocol as defined as missing three consecutive irTMS sessions or receiving less than 10 irTMS sessions during treatment at their treatment clinic will be assessed for and evaluated in data analysis.

Discontinuation of Subjects. Subjects may be discontinued from study treatment and assessments at any time. Specific reasons for discontinuing a subject from this study are: 1) Voluntary discontinuation by the subject, who is at any time free to discontinue his/her participation in the study without prejudice to further treatment; 2) Clinical deterioration: The following are objective criteria for clinical deterioration, a 25% increase in the PHQ-9 at any time during the study and/or the onset of active suicidality as assessed by the study clinicians requiring treatment outside of the study protocol; 3) Evidence of intolerable adverse reaction, or unable to tolerate irTMS or MRI; 4) Non-compliance to protocol by missing three consecutive irTMS sessions or as judged by the investigator; 5) Safety reasons as judged by the investigator.

Item 7 Risks Section:

Complete the following table to describe the risks of all **research procedures** listed in Step 2, Institutional Form (items 28-34). *Do not list risks of Routine care procedures here.*

N/A, Risks are described in the informed consent document – do not complete this table.

Research procedures

example:

- History and physical
- Questionnaire
- Laboratory tests

Add or delete rows as needed

Risks

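### The plan lets outcome assessment stop together with treatment, for reasons tied to outcome or tolerability, and does not clearly keep assessing those subjects; data may be lost informatively, with bias of unknown direction

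*Combined protocol and SAP*

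**What the plan says.** All places are in Item 6 of the combined protocol and SAP.

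- **Discontinuation of Subjects:** "Subjects may be discontinued from study treatment and assessments at any time". The listed reasons are voluntary exit; clinical deterioration (a 25% PHQ-9 increase and/or onset of active suicidality); "Evidence of intolerable adverse reaction, or unable to tolerate irTMS or MRI"; three sessions missed in a row, or the investigator's judgement of non-compliance; and safety.
- **irTMS Treatment Sessions:** of subjects who cannot tolerate the prescribed stimulation, "they will be withdrawn from the study".
- **Risk Minimization:** of a subject whose condition significantly worsens, "he or she will be withdrawn from the research protocol to continue TAU at their treatment clinic".
- **Phase III follow-up:** "One month and three months after the final irTMS treatment session, participants will be interviewed". Early stoppers are not mentioned.
- **Clinical Outcomes Data Analysis plan:** the primary efficacy outcome names weekly PHQ-9 and "the MADRS for the diagnosis of MDD assessed pre-treatment, post-treatment, and 1/3-months following the completion of treatment". The primary analysis is by mixed-effects regression. No analysis set, missing-data assumption or sensitivity analysis is given. Non-compliance (three consecutive missed sessions, or fewer than 10 received) is to be examined in the analysis.
- **Step-by-Step Methods:** 198 are randomised (66 per arm) so that 150 (50 per arm) complete the double-blind treatment phase.

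**The concern.** The trial compares three stimulation targets as assigned. That comparison needs outcomes from subjects who stop early as well as from those who finish. Here the event that ends treatment may also end measurement, and several of those events are themselves signs of how the subject is doing or how well the stimulation is tolerated. If the subjects who leave differ from those who stay in ways the recorded scores do not explain, and if this differs between arms, the estimated contrast is biased. The MADRS is the more exposed measure because its schedule in the procedures table has nothing between the baseline MRI visit and Wk 5. Once a score has not been collected, no analysis can bring it back.

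**Working it through.** **1. Planned loss.** Inputs are from Step-by-Step Methods. 66 × 3 = 198 and 50 × 3 = 150, so the totals agree. Implied loss = 198 − 150 = 48, and 48/198 = 16/66 = 24.2%. No dropout rate is stated, so the inflation cannot be traced to an input. The 48 are not divided by reason or arm, so they are a ceiling on outcome-related loss under the plan's own numbers, not an estimate of it.

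**2. What a withdrawn subject contributes.** The Table of Study Procedures has PHQ-9 at baseline, Wk 1-4, Wk 5 and Wk 8/16. It has MADRS at the baseline MRI visit, Wk 5 and Wk 8/16.

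| Leaves assessment during | PHQ-9 after baseline | MADRS after baseline |
|---|---|---|
| Week 2 | up to withdrawal | none |
| Week 4 | up to withdrawal | none |
| After Wk 5 | through Wk 5 | Wk 5 |

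**3. Size of the effect of the 25% rule.** This is an illustration by simulation, 400,000 per arm; every input except the rule, the weekly schedule, the entry threshold (PHQ-9 above 14) and the 0-27 scale is assumed.

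- Baseline PHQ-9 normal, mean 18.5, SD 3, truncated to 15-27.
- Linear four-week change, mean −6 in one arm and −3 in the other, SD 4, 5 or 6; weekly noise SD 1.5, 2.0 or 2.5.
- Withdrawal follows the first weekly PHQ-9 ≥ 1.25 × baseline, and that score is kept.
- MADRS change SD 8, correlation 0.7 with true PHQ-9 change; true contrast 5.1 or 3.0 points.

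Results:

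- The rule removes about 1-8% of the better arm and 4-16% of the worse arm.
- Week-4 PHQ-9 contrast: −2.81 to −2.98 in full data, −2.84 to −2.98 under missing-at-random estimation. There is essentially no bias, because the score that triggers withdrawal is itself recorded.
- MADRS contrast from observed subjects only, ignoring PHQ-9, if any trigger in weeks 1-4 loses the Wk 5 MADRS: 5.1 becomes 4.5-4.7 and 3.0 becomes 2.4-2.7. If only triggers in weeks 1-3 lose it: 4.6-4.9 and 2.5-2.8. The bias is about 0.2-0.6 points.
- Standard error with SD 8 and 50 per arm: 8 × √(2/50) = 1.6. The bias is therefore 0.2/1.6 ≈ 0.13 to 0.6/1.6 ≈ 0.38 of a standard error.
- Using baseline and weekly PHQ-9 to predict the missing MADRS restores the contrast (5.07-5.12 and 2.98-3.03).

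**4. Losses that no recorded score need explain.** For intolerance, suicidality, missed sessions or investigator judgement the documents give neither rates nor outcomes. What can be shown is how the sign behaves. Let m be the fraction lost in an arm and D the gap, in SD units, between the unseen outcomes and what the model predicts for them. Contrast bias = m₁D₁ − m₂D₂. The values of D, the unequal split below and the treatment of the whole implied loss as informative are all assumed.

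- Loss 16/66 in each arm, D = 0.5 in one arm only: 0.242 × 0.5 = 0.12 SD. The sign reverses if the other arm is the one affected.
- Same D = 0.5 and equal loss in both arms: 0.
- D = 0.5 in both arms, loss 10/66 against 22/66: 0.076 − 0.167 = −0.09 SD, and +0.09 SD with the arms exchanged.

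The direction depends on inputs the documents do not supply.

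**The case against.** **The only quantified harm is small and can be cured at analysis.** This stands for the 25% rule. The MADRS figure also comes from an observed-case mean, whereas the plan names mixed-effects regression without saying whether MADRS is modelled with PHQ-9. It does not answer losses through intolerance, suicidality or missed sessions, where the recorded PHQ-9 may not explain why the subject left.

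**The plan says non-compliance will be examined in the analysis.** This stands in part. It implies that some subjects with three consecutive missed sessions, or with fewer than 10 sessions, remain in the analysis, so a reader should not infer that the plan drops all early stoppers. But it promises no outcomes after stopping, and it sits uneasily with a discontinuation list that gives the same three missed sessions as a reason to leave the study.

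**The 1- and 3-month interviews run from the last session, so they could include early stoppers.** They could. The text does not say so, and the natural meaning of withdrawal from the study points the other way.

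**Unequal loss between arms is speculative.** It is not shown. All arms are active, with the same pulse protocol, the same intensity rule and robotic delivery meant to equalise experience. A reader might infer that one target will lose more subjects than another; the documents support only that this is possible, since the sites differ.

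**Continued assessment may cut across protections.** This stands, and it limits the fix. Risk Minimization stops interviews when subjects are distressed, the Research Monitor may remove a subject from the protocol, and safety is a listed reason for discontinuation.

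**Conclusion.** The gap is real and should be closed, with medium confidence. The plan allows treatment and assessment to end together for reasons linked to outcome or tolerability, uses mandatory withdrawal wording for two of those reasons, and nowhere clearly provides for later assessment.

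Three stronger readings might be inferred, and the documents do not support them:

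- **That 24.2% of subjects will be lost informatively.** The 48 include every kind of exit; only part would be outcome-related, and only part could be recovered.
- **That the 25% rule seriously distorts the primary analysis.** Under the assumed inputs it leaves weekly PHQ-9 essentially unbiased and moves a PHQ-9-blind MADRS analysis by well under half a standard error.
- **That the bias favours a particular arm or always shrinks the contrast.** The simulated shrinkage belongs to one route under one set of assumptions; the overall direction is unknown.

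The MADRS statement rests on the schedule in the procedures table and analysis plan, and applies to subjects actually withdrawn from assessment. The scale schedule in Item 4 and the timing of follow-up after extended treatment are separate matters and are not part of this point.

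**What to change.** 1. In Discontinuation of Subjects, separate stopping study treatment from stopping outcome assessment. Reconcile that paragraph with irTMS Treatment Sessions and Risk Minimization, so that stopping treatment does not by itself end assessment. Exceptions: the subject withdraws consent for assessment, or assessment is stopped for distress, for safety or on the Research Monitor's authority.
2. For early stoppers, continue weekly PHQ-9 on the original schedule, obtain PHQ-9 and MADRS at Wk 5 (by telephone if needed), and state that the 1- and 3-month follow-ups include them.
3. Analyse all randomised subjects by assigned arm using these data, use weekly PHQ-9 when modelling or imputing MADRS, and add a missing-not-at-random sensitivity analysis for what is still missing.
4. Leave the clinical reasons for stopping treatment as they are.

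**Cost.** Protocol wording, plus tracking and calls or visits for at most about 48 subjects, fewer after refusals and the exceptions above. Worsened subjects are already expected to continue usual treatment at their clinic, and telephone contact is already allowed at 1 and 3 months; using it at Wk 5 would be new.
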